Beck Depression Inventory-II (BDI-II), Hamilton Anxiety Scale (HAM-A), Hamilton Depression Rating Scale (HDRS), Brief Psychiatric Rating Scale (BPRS), Profile of Mood States, Drug Effects Questionnaire (DEQ), Addiction Research Center Inventory marijuana scale, St Mary's Hospital Sleep Questionnaire (SMHSQ)	X	X	X	X
SAFTEE	Х	Х	X (week 13 only)	X (end of trial)
ASI, World Health Organization Disability Assessment Schedule (WHODAS)	X	X (week 12 only)	X (week 13 only)	X (end of trial)
Urine for THC metabolite analysis	Х	Х	Х	Х
Vivitrol [®] administration		X (once every 4 weeks)		
MET/CBT		X		

Trial Objectives and Purpose:

Primary and Secondary Outcome Measures

Our primary outcome measures: 1) for tolerability will be the number of subjects that drop out because of SAEs and 2) for piloting efficacy will be the seven-day point prevalence cannabis abstinence at the end of medication phase and at the 3 month follow-up;

Secondary outcome measures will be 1) percentage of days of cannabis use over the study duration until the 3 month follow-up; 2) amount of cannabis use over the study duration until the 3 month follow up. 3) effects on withdrawal symptoms scores, craving scores and number of urine samples screen as positive.

Abstinence status will be also based on the urine samples collected during the trial.

PRELIMINARY RESULTS

A CUD treatment clinic has been set up at the Addiction Medicine Service (AMS)/Concurrent Outpatient Medical & Psychosocial Addiction Support Service (COMPASS) that is using the CBT-MET approach as standard of care. We have recruited subjects for pharmacotherapy trial for CUD at CAMH. Those preliminary results demonstrate the feasibility of recruiting the subjects for this study.

METHODS:

Subjects

Inclusion criteria

- Adult (18-64) male or female (gender to be analyzed as a covariate)
- Understand and willing to comply with study requirements and restrictions
- Willing to use appropriate contraceptive method throughout the study
- Otherwise healthy as judged by investigator based on medical history, physical exam, vitals, ECG and labs
- DSM 5 criteria for current CUD
- Report cannabis as primary drug of abuse
- Have cannabis positive urine drug screen
- Treatment seeking cannabis smoker

Exclusion criteria

- Meets DSM 5 diagnostic criteria for a current severe mental disorder, including substance-related and addictive disorders, other than CUD, tobacco use disorder, and caffeine-related disorders
- Unstable medical conditions

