- Pregnant or breast-feeding
- Positive urine drug test for opioids (including methadone, morphine, buprenorphine) or benzodiazepines (unless prescribed) at baseline
- Any IM gluteal administration 30 days prior to baseline
- Participation in a clinical trial of a pharmacological agent within 30 days prior to baseline
- Known intolerance and/or hypersensitivity to naltrexone, carboxymethylcellulose, or polylactide-coglycolide
- Any finding that, in the view of the principal investigator, would compromise the subject's ability to fulfill the protocol visit schedule or visit requirement (e.g. unadjudicated charges and/or pending parole hearings)

Pre-study Screening and Baseline/follow up evaluations and questionnaires that will be used:

- a) Structured Clinical Interview for DSM 5 severe mental disorders, including substance-related and addictive disorders, other than CUD, tobacco use disorder, and caffeine-related disorders.
- b) DSM 5 Criteria for CUD for the past month at baseline, end of treatment and end of follow-up
- c) Demographic assessments.
- d) Psychiatric/Medical Evaluation and Physical Examination by study physician Weight (kg) and Vital Signs (Temperature, Pulse, Blood Pressure and Respiration Rate). Carbon monoxide will be taken at each study visit to assess exposure to smoke (will reflect both cannabis and tobacco exposure).
- e) 12-lead Electrocardiogram (EKG).
- f) Blood work, including complete blood count (CBC), electrolytes, renal and liver function tests will be carried out at baseline and prior to the 2nd and 3rd Vivitrol injections.
- g) For female subjects, a serum pregnancy test (beta-HCG) at inclusion (and when deemed needed) and weekly urine pregnancy test will be performed. Female subjects will be asked if they are lactating.
- h) Ten-panel urine toxicology screen at baseline, and at each study visit to ensure absence of illicit drug use.
- i) Substance use assessment including the age of first use, age of regular use, number of days in the past 30 days that the substance was used, number of days in the past week that the substance use used, and the amount of the substance used per using day (i.e. joints per day for cannabis).

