- j) Cannabis Use will be assessed by toxicology and self-report. Participants will provide a urine sample every week (see assessment schedule). The timeline follow-back (TLFB) will be used to assessing the number of days cannabis was smoked, the amount smoked, and the amount of money spent on cannabis since their last appointment. Smoking diaries will also be completed daily outlining how much cannabis was obtained at a time, how many days that amount lasted, and what amount, if any, was shared.
- j) Addiction Severity Index self-report version.
- k) Cannabis Withdrawal will be assessed using the Marijuana Withdrawal Checklist with 16 4-point items indicating severity during the prior 24 hours [55]. Cannabis craving will be assessed using the Cannabis Craving Questionnaire (MCQ) [56].
- The sleep disturbance will be assessed using the St Mary's Hospital Sleep Questionnaire (SMHSQ), a self-report instrument developed for use with psychiatric and medical in-patients [57].
- m) The Hamilton Anxiety Scale (HAM-A), will be used to assess the affective and vegetative symptoms of anxiety [58].
- n) Depressive symptoms will be assessed using the Beck Depression Inventory-II (BDI-II a selfreport depression rating scale has been used extensively in depression treatment research [59]) and the Hamilton Depression Rating Scale (HDRS), 21-item version, a clinical administered rating scale for depression with well-established reliability and validity [60]; The Profile of Mood States [61] will also be used.
- o) Psychotic symptoms will be assessed using the Brief Psychiatric Rating Scale (BPRS)
- p) Cigarette smoking history including timeline follow-back (TLFB) for the past one week [62]; Pack-Years (average daily smoking consumption in packs per day multiplied by the years smoked); Fagerstrom Test for Nicotine Dependence (FTND).
- q) Alcohol and caffeinated beverage use TLFB for the past one week [62].
- r) The SAFTEE will be used to monitor for treatment-emergent medication side effects.
- s) Participants will complete the Drug Effects Questionnaire (DEQ). The DEQ has five items (feel, high, dislike, like, and more) measured on a 100 mm visual analog scale; the revised Addiction Research Center Inventory marijuana scale [66] will also be used
- t) The World Health Organization Disability Assessment Schedule (WHODAS) will be used to

monitor disability status at baseline and at the end of treatment and follow-up.

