Our Primary outcome measures will be: 1) tolerability which will be assessed by determining the number of participants who withdraw from the study because of SAEs and 2) pilot efficacy of this intervention will be assessed by assessing seven-day point prevalence cannabis abstinence one week after the end of medication phase; and at 3 month follow up. Secondary outcome measures will be: 1) percentage of days of cannabis use over the study duration until the 3 month follow up; 2) amount of cannabis use over the study duration until the 3 month follow up; 3) effects on withdrawal symptoms scores, craving scores and number of urine samples screen as positive and 4) DSM5 criteria for CUD at the end of treatment and follow-up as compared with baseline. Efficacy analyses of count variables (e.g. number of joints per week) will be performed using generalized estimating equations (GEEs), specifying a negative-binomial distribution for the counts. Linear mixed models will be used to analyze continuous, secondary outcome measures (e.g. mood and anxiety ratings, physiological measures). All efficacy analyses will be by intention-to-treat. Treatment week will measure changes within-subjects. Subjects will be use as a measure of abstinence in this study. Urine samples will be collected and analyzed for THC metabolites.

Procedure for accounting for missing, unused, and spurious data: In the final report the procedures used to deal with missing, unused or spurious data in statistical analyses will be described.

Procedures for reporting deviations from the original statistical plan: Any deviation from the planned statistical analyses will be described in the final report.

Power calculation: The goal is to collect pilot data to demonstrate tolerability and trend for efficacy of Vivitrol® for treatment of cannabis dependence. We are hypothesizing that the use of cannabis will decrease by at least 50% after treatment with Vivitrol®. Assuming Cannabis use of around 9.5 g (SD = 5) at baseline [as per paper], a sample of 10 subjects will give us 80% power to detect a decrease in cannabis use of 50% from baseline to the last time point. The power calculation was conducted through Monte Carlo simulation, where 5000 replications were conducted. It was also assumed that the

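### The TLFB days and amount items and the last-use question are worded for smoked cannabis, while secondary outcomes 1 and 2 are days and amount of cannabis use with no limit of route

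*Combined protocol and SAP*

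**What the plan says.** All places are in the combined protocol and SAP.

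- **Outcomes.** Primary and Secondary Outcome Measures gives the first secondary outcome as "percentage of days of cannabis use over the study duration until the 3 month follow-up" and the second as the amount of cannabis use over the same period. Data analysis repeats both. Neither is limited by route. The primary efficacy outcome is "seven-day point prevalence cannabis abstinence".
- **Main self-report instrument.** The first of the two evaluation items labelled j opens with "Cannabis Use will be assessed by toxicology and self-report". It then defines the TLFB as "assessing the number of days cannabis was smoked, the amount smoked, and the amount of money spent on cannabis since their last appointment". Days and amount are tied to smoking; money spent is not.
- **Diary.** The same item adds "Smoking diaries will also be completed daily outlining how much cannabis was obtained at a time, how many days that amount lasted", and asks what amount was shared.
- **Substance use assessment.** Item i asks for "number of days in the past 30 days that the substance was used" and for days in the past week. It gives amount per using day in joints for cannabis.
- **Last-use question.** Under Biological sample collection, the question asked at each sample concerns when the participant last smoked cannabis.
- **Urine.** The outcome section states "Abstinence status will be also based on the urine samples collected during the trial". Every sample has THC quantified and creatinine measured.
- **Population.** The inclusion criteria admit treatment seekers who smoke cannabis and have a cannabis-positive urine screen. The trial is open label, with one arm of 10.

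**The concern.** The outcomes concern cannabis use, but the instrument that would normally supply days and amount asks about smoking. The smoked wording recurs in the last-use question, in the joints unit of item i, and in the example count variable in Data analysis (joints per week). No item is worded for edible, vaporised or other non-smoked use.

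Enrolling smokers fixes the route at entry, not for the rest of the trial. Someone trying to stop smoking may keep using cannabis another way. If the form is completed as defined, that use is missing from both secondary outcomes and appears as improvement. In a single-arm pre-post design, nothing separates this from a treatment effect. The stated aim is to show a trend for efficacy ahead of later randomised trials, so an inflated reduction could carry forward into their planning.

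**Working it through.** **1. Which source can feed secondary outcomes 1 and 2?** The plan names none, so the candidates are set side by side.

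| Source | Days of use | Amount used | Limited to smoking? | In Summary of Study Assessments? |
|---|---|---|---|---|
| Cannabis TLFB | yes | yes | days and amount: yes; money: no | yes, baseline and all later visit blocks |
| Diary | indirectly (how long a supply lasted) | indirectly (obtained, shared) | by title, not by content | yes |
| Substance use assessment, item i | yes | in joints | days: no; amount unit: smoked | no row |
| Urine THC | no | no | no | yes |

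Only the TLFB is both scheduled and defined as giving days and amount, and both of those items say smoked.

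**2. The plan's own figure.** The inputs from Power calculation are baseline mean 9.5 g, SD 5, a 50% fall (4.75 g), correlation 0.6, n = 10, two-sided 0.05 and no dropout. The SD at the last time point is not given; 5 is assumed.

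- SD of the difference = √(25 + 25 − 2 × 0.6 × 25) = √20 = 4.47 g.
- With two time points, the random-intercept model with time as its only fixed effect is equivalent to a paired t-test. Power is 79.6% at n = 9 and 84.7% at n = 10.

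Ten is therefore the smallest n reaching 80%, and the stated sample size reproduces. With a last-point SD of 2.5 or 6, power at n = 10 is 91.1% or 76.2%. The present point does not change this calculation.

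**3. Effect of switching on mean amount.** Let k of the 10 subjects switch fully, with smoked-only items recording 0 g at the last time point. For switchers of average use and a true fractional fall f:

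- apparent fall = f + (k/10) × (1 − f).
- With f = 0 and k = 1, this is 9.5/10 = 0.95 g, and 0.95/9.5 = 10%.
- With f = 0.25 and k = 1, it is 0.25 + 0.1 × 0.75 = 32.5%.

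The chance of p < 0.05 with no true change comes from 20,000 simulated trials per row, using the step 2 inputs.

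| k of 10 | Apparent fall, no true change | Chance of p < 0.05, no true change | Apparent fall, true fall 25% |
|---|---|---|---|
| 0 | 0% | 5.0% | 25% |
| 1 | 10% | 4.6% | 32.5% |
| 2 | 20% | 8.4% | 40% |
| 3 | 30% | 15.9% | 47.5% |

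The values of k are assumptions. A full switcher one SD below or above the mean (4.5 g or 14.5 g) adds 4.5/95 = 4.7 or 14.5/95 = 15.3 percentage points instead of 10. A subject who moves half of an average use to another route adds 5.

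**4. Abstinence.** In the self-report part alone, one misclassified subject in 10 is 10 percentage points. That reaches the outcome only if self-report prevails over a urine sample showing THC.

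**The case against.** The strongest case against is that the plan has other routes to the truth. Money spent, the diary contents and the days-used questions in item i are not limited to smoking, and the past-week question matches the abstinence window. Urine THC does not depend on route and is part of abstinence status. The protocol only summarises the TLFB; the form itself is not in the documents. Entrants are smokers, the trial is a 10-subject pilot, and no switching rate is given.

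Much of this stands, and it rules out several stronger readings that a reader might infer:

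- **That self-report captures nothing but smoked cannabis.** It does not follow, given the items just listed.
- **That a switcher counts as abstinent, so that the trial measures smoking cessation.** This needs self-report to override urine, and no such rule is stated. The plan gives no rule for discordant results at all. The Data analysis sentence on the abstinence measure is garbled, so what it omits should be read with caution.
- **That the error can run only one way.** Non-smoked use at baseline would also go uncounted, and a mixed-route user moving towards smoking would show a spurious increase.
- **That even one switcher inflates the test.** It does not: 4.6% against a nominal 5%, because the outlying difference also widens the standard error.

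The objection does not close the gap for days and amount. Money spent is not an outcome, the diary does not directly record days or quantity used, item i has no place in the schedule and counts amount in joints, and urine gives neither quantity.

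**Conclusion.** The point holds for secondary outcomes 1 and 2. As defined, the TLFB leaves non-smoked use out of days and amount, and no other scheduled source is defined as supplying both. The resulting bias is mainly towards larger reductions.

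Its size is conditional: about 10 percentage points of apparent fall in mean amount per full switcher of average use among 10, with no true change. This assumes that the smoked-only items feed the outcome, that the switch is complete by the last time point, and that the form follows the protocol's wording. The main harm is to the estimate. The test is inflated only from about two switchers upwards (8.4%, then 15.9% for three). With a true 25% fall, three switchers would make it look like 47.5%, close to the hypothesised 50%.

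For the primary efficacy outcome, the documents support only the limited statement that its self-report part is exposed. This is a worthwhile, inexpensive improvement and does not invalidate the trial.

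**What to change.** - Reword the TLFB days and amount items, the diary and the last-use question to ask about cannabis used by any route, and record the route.
- Define percentage of days and amount of use on use by any route, name the TLFB as their source, and keep smoked use as a subset.
- Apply the same wording at baseline, so that the pre-post comparison is like for like.
- Add one sentence saying how abstinence is classified when self-report and urine disagree. This is a separate gap, but it decides whether the wording can reach the primary outcome.

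The cost is a change to a few form items and two outcome definitions, with no extra visits or samples. The real downside is that non-smoked amounts need a stated conversion to a common unit. If none is acceptable, days of use by any route can serve as the common measure, with amount reported by route.

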This project will test the safety and effectiveness of long term (i.e. 12 weeks) administration of the injectable extended-release of naltrexone; Vivitrol[®]. Vivitrol[®] is primarily used in the management of alcohol and opioid dependence. Naltrexone maintenance (e.g. oral) seems a promising treatment for cannabis use disorder (CUD). Therefore, administering Vivitrol[®] may have therapeutic properties for treatment of cannabis use disorder. The data collected will be used to ensure that the administration schedule we have planned for the subsequent future randomized clinical trials is appropriate.

In this study we will focus on the tolerability and effectiveness of the antagonist at the μ -opioid receptor, Vivitrol[®], to reduce cannabis use, increase abstinence rates and reduce cannabis withdrawal and craving.

OVERVIEW

[figure not shown]
The study will be open label, with no placebo control. Ten male and female subjects seeking treatment for cannabis dependence subjects will undergo study procedures as outlined below. Treatment with Vivitrol[®] will start at day 1 (week 1) and a target quit date will be set up at Day 7 (but subjects will be allowed to stop using cannabis before if they are willing and able to). There will be a total of 12 weeks (3 injections, 1 every 4 weeks) of exposure to Vivitrol[®]. Study visits will occur weekly during the medication phase of the study. Motivational Enhancement Therapy and Cognitive Behavioral Therapy (MET/CBT) will also start at Week 1 and therefore, all participants will receive a combination of pharmacotherapy (Vivitrol[®] 4 mL intramuscular injection) associated with MET/CBT for 12-weeks in accordance with the intervention practices shown to be effective in treatment of cannabis dependence [54]. The intervention will be adapted from the Brief Counseling for Marijuana Dependence manual published by the Substance Abuse and Mental Health Services Administration (SAMHSA). In addition, to ensure compliance a Contingency Management plan will be implemented with \$5 voucher that will be provided at each visit that is attended and at which biological samples have been provided, but with 5\$ voucher loss for a missed appointment. The vouchers will be provided at end of treatment phase and at end of the follow-up phase.

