At study visits, vital signs and self-report ratings will be collected. The subjects will have to come once per week (during treatment phase) to the center to assess cannabis and other substances usage

and will be asked to provide urine samples (see Summary of Study Assessments). As there may be compliance issues, a contingency management approach will be also implemented.

Following the medication phase, participants will have a follow-up weekly for another four weeks and then monthly until the 3 month follow up visit after the treatment starting date. We are planning to enroll 10 subjects.

Study Flow Schema

*Please see Summary of Study Assessments for tests administered during this period

Subjects will be pre-screened initially during a telephone interview in which basic medical, psychiatric, and substance abuse histories will be obtained without personal identifiers, contact information will be collected only for eligible participants as for pre-screening. The qualified subjects will then be assessed using the Structured Clinical Interview for *DSM 5* (SCID) and we will assess presence of CUD using *DSM 5* criteria. We will enroll a total of 10 subjects, that will be treated open-label (non blinded) with Vivitrol 380 mg.

Experimental group	Experimental condition	
Group #1 (n=10)	Vivitrol® 380 mg, 4 mL intramuscular injection + MET/CBT	

Summary of Study Assessments

Assessment	Baseline	Weekly (Weeks 1-12)	Weekly (Weeks 13-16)	Monthly (months 5-6)
Informed Consent	X			
Psychiatric Evaluation (including				
SCID)	Х			
DSM5 criteria for CUD	Х	X (week 12 only)	X (week 13 only)	X (end of trial)
Demographic	Х	· · · ·		
Bloodwork (including CBC),		X (prior to 2 nd and 3 rd		X (end of trial)
Urinalysis	Х	Vivitrol injections)		
EKG	Х	X (week 1 only)		X (end of trial)
Physical Exam	Х			X (end of trial)
Urine Toxicology	X	X (before Vivitrol administration)	Х	Х
Vital Signs, Carbon Monoxide	Х	Х	Х	Х
Serum Pregnancy Test (Females only)	Х	If needed	If needed	If needed
Urine Pregnancy Test (Females only)	Х	Х	Х	Х
FTND, Cigarette, alcohol and caffeine Time-line Follow-Back (TLFB)	Х	Х	X	X
Smoking Diary	Х	Х	Х	Х
Cannabis TLFB, Marijuana withdrawal checklist (MWC), Marijuana Craving Questionnaire (MCQ)	Х	Х	Х	X

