Female participants will be required to take measures to avoid becoming pregnant during the study. Acceptable contraceptive methods include: barrier methods of contraception (e.g. male condom, female condom, cervical cap, diaphragm, contraceptive sponge).

Note: No barrier method by itself achieves a highly effective standard of contraception. The proper use of diaphragm or cervical cap includes use of spermicide and is considered one barrier method. The cervical cap and contraceptive sponge are less effective in parous women. The use of spermicide alone is not considered a suitable barrier method for contraception.

When used consistently and correctly, "double barrier" methods of contraception (e.g. male condom with diaphragm, male condom with cervical cap) can be used as an effective alternative to the highly effective contraception methods described below. The consistent and correct use of a male condom in

association with spermicide may be considered an acceptable barrier method in some clinical trial settings, for this study the above decision will be at the discretion of the study physician.

Female participants that underwent or currently using highly effective methods of contraception (i.e. hormonal contraceptives, intrauterine device (IUD) or intrauterine system (IUS)), will be also eligible for the trial.

Potential participants will be informed of these and other additional information regarding study medication during the informed consent process.

Other warnings and precautions to follow with Vivitrol® include:

Vulnerability to Opioid Overdose: Following Vivitrol® treatment opioid tolerance is reduced from pretreatment baseline, and patients are vulnerable to potentially fatal overdose at the end of a dosing interval, after missing a dose, or after discontinuing Vivitrol® treatment. Attempts to overcome blockade may also lead to fatal overdose (see product information for Vivitrol® for more detail).

Injection Site Reactions: In some cases, injection site reactions may be very severe. Some cases of injection site reactions required surgical intervention see product information for Vivitrol® for more detail).

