Advise patients that they may experience nausea following the initial injection of Vivitrol®. These episodes of nausea tend to be mild and subside within a few days post-injection. Patients are less likely to experience nausea in subsequent injections. Patients should be advised that they may also experience tiredness, headache, vomiting, decreased appetite, painful joints and muscle cramps.

Advise patients that because Vivitrol® is an intramuscular injection and not an implanted device, once Vivitrol® is injected, it is not possible to remove it from the body.

Advise patients that Vivitrol[®] has been shown to treat alcohol and opioid dependence only when used as part of a treatment program that includes counseling and support.

Advise patients that dizziness may occur with Vivitrol® treatment, and they should avoid driving or operating heavy machinery until they have determined how Vivitrol® affects them.

Other events were observed during the Vivitrol® Clinical Studies (in alcohol- and/or opioid-dependent subjects treated with Vivitrol®), including events for which a drug cause was remote, events that were so general as to be uninformative, and those events reported only once that did not have a substantial probability of being acutely life-threatening (see product information for Vivitrol® for more detail).

Adverse Events Reporting

In the event of a serious adverse event (SAE), whether related to study drug or not, the Principal / Qualified investigator will notify REB of its occurrence and will submit the necessary documentation to their attention within timelines provided in CAMH SOP HSR207 Serious Adverse Event (SAE) Reporting. Only SAEs that are Serious unexpected adverse drug reaction (SUADR) will be reported to Health Canada as outlined in ICH E2A Clinical Safety Data Management Definitions and Standards for Expediting Reporting. While only SAEs and SUADRs will be reported as documented above, every adverse event will be assessed and recorded in the subject's research record by research staff working on the study and reviewed regularly by the Principal/Qualified Investigator. AEs will be documented and reported as mandated by current regulations.

The trial will be conducted in compliance with protocol, GCP, and applicable regulatory requirements.

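### Structured side-effect elicitation with the SAFTEE is missing from four attended follow-up visits (weeks 14, 15, 16 and month 5), and no opioid-use or overdose question is scheduled there

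*Combined protocol and SAP*

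**What the plan says.** Item r of the list of screening, baseline and follow-up evaluations gives the purpose of the SAFTEE: "The SAFTEE will be used to monitor for treatment-emergent medication side effects". No other entry in that list is described in those terms. In the Summary of Study Assessments the SAFTEE is marked at baseline and weekly in weeks 1-12. In the column for weeks 13-16 it is limited to week 13, and in the column for months 5-6 it is limited to the end of the trial.

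On dosing, the Overview states: "There will be a total of 12 weeks (3 injections, 1 every 4 weeks) of exposure to Vivitrol". On follow-up, the narrative states that "participants will have a follow-up weekly for another four weeks and then monthly until the 3 month follow up visit after the treatment starting date".

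Among the warnings in the risk section, the paragraph on opioid overdose says that "patients are vulnerable to potentially fatal overdose at the end of a dosing interval, after missing a dose, or after discontinuing" treatment. The section on adverse event reporting says that "every adverse event will be assessed and recorded in the subject's research record by research staff working on the study". It attaches no instrument, question or visit schedule to that duty.

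**The concern.** Subjects keep attending after the last dosing interval and complete the craving, mood, sleep and drug-effect scales, but at most of these visits nobody is scheduled to go through side effects with them in a structured way. The protocol describes tolerability as one focus of the study and says that the risks of this drug in cannabis use disorder are still unknown, so a fuller record of side effects after treatment has value.

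Two things are at stake. First, non-serious complaints that arise or persist after the last injection (injection-site, hepatic or other somatic symptoms) would depend at four visits on what subjects volunteer or staff happen to notice. Collection that falls from weekly to occasional can also look like a fall in events once treatment stops. Second, the protocol itself identifies the time after discontinuation as one of opioid vulnerability, but schedules no direct question about opioid use or overdose at these visits.

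**Working it through.** No power, sample-size or error-rate figure is involved. The check is a visit count and a comparison of rows in the assessment table.

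**Visits without the SAFTEE**
- Weekly follow-up visits: weeks 13, 14, 15 and 16, so 4 (table and narrative agree on this number).
- Monthly follow-up visits: months 5 and 6, so 2. This assumes one visit per month, with month 6 as the end of the trial.
- Follow-up visits in total: 4 + 2 = 6.
- SAFTEE marked: week 13 and end of trial, so 2.
- Not marked: 6 − 2 = 4 (weeks 14, 15, 16 and month 5).
- Over 10 subjects, if all attend: 4 × 10 = 40 visits.

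**Position relative to dosing**
- Three injections at 4-week intervals fall in weeks 1, 5 and 9, and the last interval covers weeks 9-12.
- The week 13 visit, at about day 12 × 7 + 1 = 85, falls at the end of the last interval. The four visits without the SAFTEE all come later.

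**Length of the gap, by the table**
- End of month 6 is about day 6 × 28 = 168 to day 26 × 7 = 182.
- Gap from week 13: 168 − 85 = 83 days to 182 − 85 = 97 days, or about 12 to 14 weeks, against 1 week during treatment.
- This rests on the months 5-6 column. Three months after the treatment start is about week 13, so the narrative's end point would arrive before its own four further weekly visits were finished. The two passages cannot both hold as written.

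**Intensity of elicitation**
- Treatment: 12 administrations in 12 weeks, or 1 per week.
- Follow-up, by the table: 2 administrations in about 12 to 14 weeks, so 2/14 = 0.14 to 2/12 = 0.17 per week.
- The documents state no look-back period for the SAFTEE, so the end-of-trial administration cannot be assumed to cover the whole interval.

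**What else is scheduled at the four visits**
- Marked in both follow-up columns: urine toxicology, vital signs, BDI-II, HDRS, HAM-A, BPRS, Profile of Mood States, DEQ and the sleep questionnaire.
- Not at these visits: after the third injection, bloodwork is next marked at end of trial. Physical examination (after baseline) and EKG (after week 1) are likewise marked only at end of trial. The ASI follows the same week 13 and end-of-trial pattern as the SAFTEE.
- The DEQ has five items on drug effect and liking, so it does not cover somatic complaints.
- The scheduled timeline follow-backs cover cigarettes, alcohol, caffeine and cannabis, not opioids. Item i describes a general substance-use assessment, but the table has no row for it and so gives it no follow-up visit.

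**The case against.** The strongest reply is that this is a reasonable taper for a 10-subject open-label pilot: weekly during exposure, once just after it, and once at the end. Nothing in the documents contradicts that choice. Several parts of the reply stand.

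- Safety monitoring does not stop. Toxicology can signal opioid re-use, although the contents of the ten-panel screen are not listed. The depression scales bear directly on the depression warning, and bloodwork and a physical examination at end of trial give some hepatic information.
- Staff see subjects at all four visits and must record every adverse event, with regular review by the Principal/Qualified Investigator.
- The primary tolerability outcome is the number of subjects who drop out because of SAEs, which does not use the SAFTEE. No comparison of event rates on and after treatment is planned.

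A reader might infer that systematic safety collection ends just as the window for fatal overdose opens. The documents do not support that. Nothing says that the SAFTEE asks about opioid use or overdose. The ends of the first two dosing intervals fall within weekly SAFTEE collection, and the week 13 administration falls at the end of the third. Opioid-positive urine at baseline is an exclusion, and the corresponding counselling point is addressed to people who previously used opioids. An overdose would also probably surface as an SAE.

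The reply does not remove the gap. The recording duty does not say how events are to be elicited in follow-up, and none of the scales that continue is described as covering injection-site or hepatic complaints.

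**Conclusion.** The point holds as a modest one. By the table, and assuming one visit per month, 4 of 6 follow-up visits have no structured side-effect elicitation. The omissions in weeks 14-16 rest on the four weekly visits that both table and narrative provide. The month 5 omission and the gap of 12 to 14 weeks rest on the months 5-6 column alone and remain provisional until the follow-up end point is reconciled.

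The consequence is thinner ascertainment of non-serious injection-site, hepatic and other somatic complaints, and adverse-event counts that cannot be compared between the treatment and follow-up periods. Separately, opioid use and overdose at these visits are left to urine toxicology and general adverse-event recording. It would go too far to conclude that the primary tolerability result is biased, that adverse events go unrecorded, or that the SAFTEE schedule itself leaves overdose undetected.

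**What to change.** - In the SAFTEE row of the Summary of Study Assessments, mark every visit in weeks 13-16 and each monthly visit.
- Add a row for a brief question on opioid use and overdose since the last visit, at the same visits. It is needed separately because the documents do not show that the SAFTEE covers this.
- Reconcile the months 5-6 column with the narrative's end of follow-up, so that the number and timing of these visits are fixed.
- If the present SAFTEE schedule is kept, state the reason and say that adverse events on and after treatment will be reported separately, with the number of SAFTEE administrations in each period, and not compared.

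The cost is an edit to the table and a few minutes per existing follow-up visit. For the SAFTEE this means at most 4 extra administrations per subject, or 40 in all. No new visits are needed.
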